Annex 1 THE WHOQOL-BREF

ABOUT YOU

I.D. number

Before you begin we would like to ask you to answer a few general questions about yourself: by circling the correct answer or by filling in the space provided.

What is your gender? Male Female

Male Female

What is your **date of birth**? _____ / _____ / _____

_____ / _____ / _____

Day / Month / Year

What is the highest education you received?	None at all
	Primary school
	Secondary school
	Tertiary

What is your marital status?	Single	Separate
	Married	d
	Living as married	Divorced

Are you currently ill? Yes No

If something is wrong with your health what do you think it is?

Instructions

This assessment asks how you feel about your quality of life, health, or other areas of your life. **Please answer all the questions.** If you are unsure about which response to give to a question, **please choose the one** that appears most appropriate. This can often be your first response.

Please keep in mind your standards, hopes, pleasures and concerns. We ask that you think about your life **in the last two weeks**. For example, thinking about the last two weeks, a question might ask:

	Do you get the kind of support from othersthat you need?	Not at all 1	Not much 2	Moderatel y3	A great deal 4	Completely 5
--	--	-----------------	---------------	-----------------	-------------------	-----------------

You should circle the number that best fits how much support you got from others over the last two weeks. So you would circle the number 4 if you got a great deal of support from others as follows.

	Do you get the kind of support from others that you need?	Not at all 1	Not much 2	Moderately 3	A great deal 4	Completely 5
--	---	-----------------	---------------	-----------------	-------------------	-----------------

You would circle number 1 if you did not get any of the support that you needed from others in the last two weeks. Please read each question, assess your feelings, and circle the number on the scale for each question that gives the best answer for you.

THE WHOQOL-BREF

		Very poor	Poor	Neither poor nor good	Good	Very good
1 (G1)	How would you rate your quality of life?	1	2	3	4	5

		Very dissatisfied	Dissatisfied	Neither satisfied nor dissatisfied	Satisfied	Very satisfied
2 (G4)	How satisfied are you with your health?	1	2	3	4	5

The following questions ask about **how much** you have experienced certain things in the last two weeks.

		Not at all	A little	A moderate amount	Very much	An extreme amount
3 (F1.4)	To what extent do you feel that (physical) pain prevents you from doing what you need to do?	1	2	3	4	5
4 (F11.3)	How much do you need any medical treatment to function in your daily life?	1	2	3	4	5
5 (F4.1)	How much do you enjoy life?	1	2	3	4	5
6 (F24.2)	To what extent do you feel your life to be meaningful?	1	2	3	4	5

		Not at all	A little	A moderate amount	Very much	Extremely
7 (F5.3)	How well are you able to concentrate?	1	2	3	4	5
8 (F16.1)	How safe do you feel in your daily life?	1	2	3	4	5
9 (F22.1)	How healthy is your physical environment?	1	2	3	4	5

The following questions ask about **how completely** you experience or were able to do certain things in the last two weeks.

		Not at all	A little	Moderately	Mostly	Completely
10 (F2.1)	Do you have enough energy for everyday life?	1	2	3	4	5
11 (F7.1)	Are you able to accept your bodily appearance?	1	2	3	4	5
12 (F18.1)	Have you enough money to meet your needs?	1	2	3	4	5
13 (F20.1)	How available to you is the information that you need in your day-to-day life?	1	2	3	4	5
14 (F21.1)	To what extent do you have the opportunity for leisure activities?	1	2	3	4	5

		Very poor	Poor	Neither poor nor good	Good	Very good
15 (F9.1)	How well are you able to get around?	1	2	3	4	5

The following questions ask you to say how **good or satisfied** you have felt about various aspects of your life over the last two weeks.

		Very dissatisfied	Dissatisfied	Neither satisfied nor dissatisfied	Satisfied	Very satisfied
16 (F3.3)	How satisfied are you with your sleep?	1	2	3	4	5
17 (F10.3)	How satisfied are you with your ability to perform your daily living activities?	1	2	3	4	5
18 (F12.4)	How satisfied are you with your capacity for work?	1	2	3	4	5
19 (F6.3)	How satisfied are you with yourself?	1	2	3	4	5
20 (F13.3)	How satisfied are you with your personal relationships?	1	2	3	4	5
21 (F15.3)	How satisfied are you with your sex life?	1	2	3	4	5
22 (F14.4)	How satisfied are you with the support you get from your friends?	1	2	3	4	5

23 (F17.3)	How satisfied are you with the conditions of your living place?	1	2	3	4	5
24 (F19.3)	How satisfied are you with your access to health services?	1	2	3	4	5
25 (F23.3)	How satisfied are you with your transport?	1	2	3	4	5

The following question refers to **how often** you have felt or experienced certain things in the last two weeks.

		Never	Seldom	Quite often	Very often	Always
26 (F8.1)	How often do you have negative feelings such as blue mood, despair, anxiety, depression?	1	2	3	4	5

Did someone help you to fill out this form?.....

How long did it take to fill this form out?.....

Annex 2

**Health Questionnaire**

Mark with a cross in the corresponding chart for each group, the answer that best describes your state of health today.

Mobility

I don't have trouble walking

I have some trouble walking

I've got to be in bed

Personal Care

I don't have a problem with self-care

I have some trouble bathing or dressing

I am unable to bathe or dress myself

Activities of Daily Living (e.g., working, studying, housework, family activities, or recreational activities)

I have no problem going about my daily activities

I'm having some trouble doing my daily activities

I am unable to carry out my daily activities

Pain / Discomfort

I have no pain or discomfort

I have moderate pain or discomfort

I'm in a lot of pain or discomfort

Distress / Depression

I'm not distraught or depressed

[figure not shown]
I am moderately distressed or depressed

I am very distressed or depressed

To help people describe how good or bad their state of health is, we have drawn a scale similar to a thermometer in which 100 is the best state of health imaginable and 0 is the worst state of health imaginable.

We would like you to tell us on this scale, in your opinion, how good or bad your state of health is today. Please draw a line from the black box where it says "Your health status today" to the point on the thermometer that in your opinion indicates how good or bad your health is today.

**Your Health Status
Today**

The best state of health imaginable

Annex 3: Cost-effectiveness Questionnaires

**Questionnaire for Survey of Associated
Indirect Costs Treatment of
Chagas Disease in Adults**

1. General data

Education: | | | 1-Unliterate, 2-incomplete elementary school, 3- complete elementary school, 4- High school, 5- Complete higher education, 6- other [specify]:
99- Not informed

2. locomotion

- Distance between the place of residence and the health center? | | | | | kms
- Means of locomotion to the health center | | | 1- on foot, 2- bicycle, 3- bus, 4- train, 5-car, 6- other [specify]:
- Commuting time between the place of residence and the health center | | | hours and | | | minutes
- Was there spending on displacement between the place of residence and the health center?
| | 1- Yes, 2- No, 99- Not informed
- If there were costs, what was the cost of commuting between the place of residence and the health center? (In local currency):

3. Accommodation for the health center appointment

- ❑ Did you need an accommodation | | 1- Yes, 2- No, 99- Not informed
- ❑ If you needed a stay, did you have any financial cost with the stay? | | 1- Yes, 2- No, 99- Not informed
- ❑ If you had costs, what is the cost of the stay? (In local currency) :
- ❑ Distance between the place of stay and the health center? | | | | kms
- ❑ Means of locomotion from the place of stay to the health center | | | 1- walking, 2- bike, 3- bus, 4-train, 5-car, 6-other [specify]:
- ❑ Travel time between the place of stay and the health center: | | hours and | | minutes.

4. Food to go to the health center

- ❑ Did it take any personal spending on food to go to the health center? | | 1- Yes, 2-No, 99- Not informed
- ❑ If there was, what is spent on food (in local currency) :

5. income

- What is your profession?
- What is your average monthly income (in local currency)? | |
- How many people depend on this income? | |
- Do you have any health insurance? | | 1- Yes, 2-No, 99-Not informed
- If you have health insurance, have there been any reimbursement for this | |
1- Yes, 2-No, 99- Not informed
- If there was a refund, what percentage of reimbursement for this service? | | | |
- Have you lost income for your current health situation? | | (1= Yes, 2=No, 99=N/I)
- If lost, how much was average loss of monthly income (in local currency)?
- If you lost income, for how many months? | | | |

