8.2 Baseline visit

At baseline (Day 0) the following assessments will be performed before the first dose of medication is administered, to obtain baseline safety data and data for further comparative analyses and multiple parameter correlations:

- Physical examination (including weight);
- Vital signs: axillary temperature, blood pressure and pulse rate;
- WHOQOL Bref, EQ-5D-3L and cost-effectiveness questionnaires will be distributed and will be completed by the participant (See Annexes 1, 2 and 3, respectively).

Concomitant medications at baseline will be recorded in the appropriate CRF.

The participant's eligibility criteria evaluation will be performed at day 0, or when the investigator has access to all results necessary for the participant's inclusion/exclusion evaluation. After participant eligibility is confirmed, randomization will occur, and the participant will receive the first kit of medication at the clinic.

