8.5 Follow up visit

During the follow-up phase, visits will be made every six months, regardless of the assigned study branch. At each visit, the following will be carried out: directed anamnesis, physical examination, EKG and determination of the parasitic DNA by PCR. Depending on evolutionary electrocardiographic changes and availability, an echocardiogram may also be requested. The times of visits will be in month 1, 4, 6, 8, 12 and 18 after the end of treatment (with a window of +/- 10 days).

EQ-5D-3L and cost-effectiveness questionnaires will be distributed to and completed by the participant during each visit.

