8.6 End of study visit

At the end of the follow-up of each participant, coinciding with month 24 (+/- 15 days) after the end of treatment, a directed anamnesis, physical examination, EKG, determination of the parasite DNA by PCR and serology will be performed and changes in concomitant medication will be recorded. Depending on evolutionary electrocardiographic changes and availability, an echocardiogram may also be requested. WHOQOL BREF and EQ-5D-3L questionnaires will be distributed to and completed by the participant.

9. Pharmacovigilance

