An economic evaluation alongside the primary clinical trial will be conducted following the International Society for Pharmacoeconomics and Outcomes Research, Inc (ISPOR) recommendations. The use of all types of resources within the clinical trial will be collected prospectively at the participant-level to assess the individual direct and indirect costs through study forms and electronic medical records. The collected protocol-driven resource use will be reviewed to allow estimation to reflect the future real-world resource use. Individual participant-level data regarding units of resources (e.g. medical visits, diagnostic tests, drugs, hospitalization) will also include all the procedures associated with the management of AE. There will be an effort to include medical and non-medical resources (e.g. transportation, absence from work). The full list of resource units will be pilot tested in each study site to investigate the feasibility.

A valuation procedure will be conducted to provide country-specific data that will be assigned for all unit costs. The imputation of available information from the most similar setting will be considered should country-specific data not be available.

The obtainment of the number of units used per-participant and the value of each unit will allow the inclusion of costs incurred at participant-level in the database for the study interventions.

Incremental cost-effectiveness ratios (ICER) will be obtained by dividing the incremental cost by the incremental health benefit. This means that the ICER will be calculated using the costs of reduced BZN treatment minus the cost of the standard treatment for chronic CD as numerator, and the effectiveness of reduced BZN treatment minus the effectiveness of the standard treatment as denominator.

The outcome of the cost-effectiveness study will be the cost per QALY gained. The QALYs will be obtained after the multiplication of years lived after each intervention by the utility values of each health state lived within the study duration.

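### The Annex 3 income-loss items have no recall period but are repeated at 10 or 11 visits, so the same loss can be counted more than once

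*Protocol*

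**What the plan says.** Part 5 (income) of Annex 3 has three linked items. The first asks "Have you lost income for your current health situation". The second asks, if so, "how much was average loss of monthly income (in local currency". The third asks "If you lost income, for how many months". The only anchor is the participant's current health situation. No item names a period or a starting point, and the duration is asked in months.

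The same form is used repeatedly:
- **Baseline (Section 8.2):** "WHOQOL Bref, EQ-5D-3L and cost-effectiveness questionnaires will be distributed and will be completed by the participant".
- **Treatment visits (Section 8.3):** the form is completed at weeks 2, 4 and 8.
- **Follow-up visits (Section 8.5):** "EQ-5D-3L and cost-effectiveness questionnaires will be distributed to and completed by the participant during each visit", and "The times of visits will be in month 1, 4, 6, 8, 12 and 18 after the end of treatment".
- **Month 24:** Section 8.6 lists only two instruments, "WHOQOL BREF and EQ-5D-3L questionnaires will be distributed to and completed by the participant", and leaves out the cost form. The cost-questionnaire row of the schedule in Section 12 also marks the end visit.

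Section 10.10 takes direct and indirect costs at participant level from study forms and electronic medical records. It does not say how repeated income answers are combined.

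**The concern.** A question repeated over time gives a total only if each answer covers a known stretch of time. Here it does not. Someone who lost income earlier can give the same answer at each later visit and be correct each time. People with a chronic infection may also have lost income to their health before enrolment, and nothing in the items keeps that apart from loss during the trial.

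The unit adds to the difficulty. An answer in months cannot be placed within an interval of two or four weeks.

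At stake are the indirect-cost part of cost per patient in each arm, and the incremental cost that uses it. A later analysis rule can decide how to treat the answers. It cannot supply a reference period that participants were never asked about.

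**Working it through.** **Number of forms.** Section 8 gives 5 visits up to the end of treatment and 7 afterwards: 5 + 7 = 12. Without screening that leaves 11. The schedule gives the same count: 1 baseline + 3 treatment + 6 follow-up + 1 end visit = 11. If Section 8.6 governs month 24, the count is 1 + 3 + 6 = 10.

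**Spacing.** With the end of treatment at day 56 and 30.4375 days per month, the 11 forms fall at 0, 0.46, 0.92, 1.84, 2.84, 5.84, 7.84, 9.84, 13.84, 19.84 and 25.84 months. The first four gaps are 0.46, 0.46, 0.92 and 1.0 months.

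**Same answers, different truths.** Suppose a participant reports no loss up to week 4, then 1 month at week 8 and 1 month at the month 1 visit. This fits one month lost between weeks 4 and 8 and reported twice (true total 1). It also fits one month lost in each interval (true total 2), since the intervals last 0.92 and 1.0 months. The form cannot tell these apart.

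**Size under different scoring rules.** The protocol states no rule, so the cases below are assumptions. The ratio is the months counted divided by the months truly lost.

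*(a) Each form reports months lost to date, and all answers are summed:*

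| Loss | Sum over 11 forms | Ratio, 11 forms | Ratio, 10 forms |
|---|---|---|---|
| 3 months, ended at baseline | 3 × 11 = 33 | 33/3 = 11.0 | 30/3 = 10.0 |
| 1 month from day 0 | 0.46 + 0.92 + 1 × 8 = 9.38 | 9.4 | 8.38/1 = 8.4 |
| 2 months from day 0 | 0.46 + 0.92 + 1.84 + 2 × 7 = 17.22 | 17.22/2 = 8.6 | 15.22/2 = 7.6 |
| 6 months from day 0 | 0.46 + 0.92 + 1.84 + 2.84 + 5.84 + 6 × 5 = 41.90 | 41.90/6 = 7.0 | 35.90/6 = 6.0 |

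*(b) The loss is reported only while it is still going on, and answers are summed:*
- 2 months from day 0: 0.46 + 0.92 + 1.84 = 3.22, ratio 3.22/2 = 1.6.
- 6 months from day 0: 0.46 + 0.92 + 1.84 + 2.84 + 5.84 = 11.90, ratio 11.90/6 = 2.0.
- 6 months starting 3 months before baseline: 3 + 3.46 + 3.92 + 4.84 + 5.84 = 21.06, ratio 21.06/6 = 3.5.

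*(c) Reports are cumulative, and only the last or largest answer is used:* ratio 1.0 for a single episode. This rule still takes in loss before baseline, and it misses a second episode if the answers are not cumulative.

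**With a window.** If each post-baseline form covers only the time since the previous one, each lost month is counted once (ratio 1.0). Loss before baseline then adds 0 to on-study cost.

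**The case against.** The strongest reply is that no passage says the answers are summed, and a combining rule is something a statistical analysis plan may hold. The wording about the current health situation may lead people to stop reporting a loss once the problem has resolved. Answers are tied to visits and can be compared with the baseline answer. Section 10.10 also draws on other study forms and medical records, and says the resource list will be pilot tested. The objective is exploratory.

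Much of this stands. Repeat counting is a risk and not a planned step, the upper ratios need the worst reading of both answers and scoring, and comparison with baseline recovers part of the information. What remains is that the collection form never asks for the period. Annex 3 is the only income form shown, and nothing in the protocol indicates that medical records hold lost income.

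Three stronger readings are tempting, and the documents do not support them:
- **A week-2 loss from adverse events is counted tenfold.** The week-2 visit is day 14, so a full month of treatment-related loss cannot have occurred by then.
- **Repeat counting favours the short regimens.** Section 6.1 gives all arms the same benznidazole dose for the first two weeks, so early loss gives no expected difference. The 20% interruption on standard treatment and the assumed halving in Section 10.1 concern treatment, not income. Randomisation balances loss before baseline on average.
- **The cost-effectiveness ratio will be unstable because the QALY difference is near zero.** The protocol defines the ratio ("Incremental cost-effectiveness ratios (ICER) will be obtained by dividing the incremental cost by the incremental health benefit") but gives no expected QALY difference or spread. How an unstable ratio would be handled may sit in the analysis plan that is not shown.

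**Conclusion.** The point holds as a defect of the questionnaire. The income-loss items have no reference period, are counted in months, and are repeated at 10 or 11 visits. The same loss can be recorded more than once, and loss before randomisation can enter as on-study loss.

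The size cannot be fixed from the protocol. For a single loss it runs from 1.0 times (cumulative reports, last or largest answer used), through about 1.6 to 3.5 times (ongoing loss only, summed), to 7 to 11 times (cumulative reports summed over 11 forms; 6 to 10 over 10 forms). These figures rest on assumed loss patterns and on every form being completed. No direction of bias between the arms is shown.

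The consequence is limited to the exploratory cost-effectiveness objective. The primary efficacy analysis and the safety comparison are not touched. It is a minor point, but the correction has to be made before the data are collected.

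**What to change.** 1. In Annex 3, for every form after baseline, begin the income-loss items with *since your last study visit* and record the duration in days or weeks.
2. Keep the open-period wording at baseline only, and report those answers separately.
3. State that only post-baseline answers are summed as on-study income loss.
4. Reconcile Sections 8.6 and 12 on whether the form is given at month 24. With the new wording, leaving it out would lose the interval from month 18 to month 24.

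The cost is a small change to the questionnaire and the electronic case report form, with the approvals that Section 13 requires for an amendment. Forms already completed would follow the old wording and need to be flagged in the analysis.
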